
This trial will be conducted in accordance with this Clinical Study Plan, the Declaration of Helsinki, ISO 14155:2011 standards and the appropriate local legislation(s). The most stringent requirements, guidelines or regulations must always be followed. The conduct of the trial will be approved by the appropriate Ethics Committee (EC) of the respective clinical site and as specified by local regulations.

**PROTOCOL ABT-CIP-10398 XIENCE 28 Global Study****PROTOCOL SUMMARY:**

Trial Name and Number	XIENCE 28 Global Study: ABT-CIP-10398
Title	XIENCE 28 Global Study
Trial Device	
The commercially approved XIENCE family of coronary drug-eluting stents¹ manufactured by Abbott Vascular, Inc, Santa Clara, USA, including:
 
 • XIENCE Xpedition (stent diameter 2.5, 2.75, 3.0, 3.25, 3.5 and 4.0 mm, stent length 8, 12, 15, 18, 23 and 28 mm), XIENCE Xpedition SV (stent diameter 2.25 mm, stent length 8, 12, 15, 18, 23, 28 mm) and XIENCE Xpedition LL Everolimus Eluting Coronary Stent System (stent diameter 2.5, 2.75, 3.0, 3.25, 3.5 and 4.0 mm, stent length 33 and 38 mm). • XIENCE Alpine Everolimus Eluting Coronary Stent System: stent diameter 2.25, 2.5, 2.75, 3.0, 3.25, 3.5 and 4.0 mm; stent length 8, 12, 15, 18, 23, 28, 33, and 38 mm. Stent lengths 33 mm and 38 mm are not available for 2.25 mm diameter stent. • XIENCE PRO^X Everolimus Eluting Coronary Stent System²: stent diameter 2.25, 2.5, 2.75, 3.0, 3.25, 3.5 and 4.0 mm; stent length 8, 12, 15, 18, 23, 28, 33, and 38 mm. Stent lengths 33 mm and 38 mm are not available for 2.25 mm diameter stent. • XIENCE PRO^A Everolimus Eluting Coronary Stent System³: stent diameter 2.25, 2.5, 2.75, 3.0, 3.25, 3.5 and 4.0 mm; stent length 8, 12, 15, 18, 23, 28, 33, and 38 mm. Stent lengths 33 mm and 38 mm are not available for 2.25 mm diameter stent. 
XIENCE Sierra Everolimus Eluting Coronary Stent System: stent diameter 2.25, 2.5, 2.75, 3.0, 3.25, 3.5 and 4.0 mm; stent length 8, 12, 15, 18, 23, 28, 33, and 38 mm.
 
Only stents up to 38 mm can be used. The above listed XIENCE stents will hereinafter be called “XIENCE” in this trial.

Objective	The primary objective of this trial is to further evaluate safety of 1-month (as short as 28 days) dual antiplatelet therapy (DAPT) in subjects at high risk of bleeding (HBR) undergoing percutaneous coronary intervention (PCI) with XIENCE.

¹ For each geography included in the trial, only approved and commercial available XIENCE stent(s) in that geography will be used.

² XIENCE PRO^X is a rebrand of the XIENCE Xpedition Stent System.

³ XIENCE PRO^A is a rebrand of the XIENCE Alpine Stent System.

**PROTOCOL ABT-CIP-10398 XIENCE 28 Global Study**

Targeted Number of Subjects	[REDACTED]
Clinical Trial Design	A prospective, single arm, multi-center, open label, non-randomized trial to further evaluate the safety of 1-month (as short as 28 days) DAPT in HBR subjects undergoing PCI with XIENCE.
Primary Endpoint	Net Adverse Clinical Endpoint (NACE, a composite rate of all-cause death, all myocardial infarction (modified ⁴ Academic Research Consortium [ARC]), stent thrombosis (ARC definite or probable), stroke or major bleeding (Bleeding defined by the Bleeding Academic Research Consortium [BARC] type 2-5) from 1 to 6 months
Secondary Endpoints	
The following endpoints will be assessed from 1 to 6 months:
 
 • Stent thrombosis (ARC definite/probable, ARC definite) • All death, cardiac death, vascular death, non-cardiovascular death • All myocardial infarction (MI) and MI attributed to target vessel (TV-MI, modified ARC) • Composite of cardiac death or MI (modified ARC) • Composite of all death or all MI (modified ARC) • All stroke, ischemic stroke and hemorrhagic stroke • Clinically-indicated target lesion revascularization (CI-TLR) • Clinically-indicated target vessel revascularization (CI-TVR) • Target lesion failure (TLF, composite of cardiac death, TV-MI and CI-TLR) • Target vessel failure (TVF, composite of cardiac death, TV-MI and CI-TVR) • Bleeding defined by the Bleeding Academic Research Consortium (BARC) type 2-5 and type 3-5 
The primary endpoint of NACE and all the above secondary endpoints will also be assessed from 6 months to 12 months and from 1 month to 12 months, respectively.

⁴ Patients present any of the following clinical or imaging evidence of ischemia (symptoms of ischemia; ECG changes indicative of new ischemia - [new ST-T changes or new LBBB], development of pathological Q waves; or imaging evidence of a new loss of viable myocardium or a new regional wall motion abnormality), AND confirmed with elevated cardiac biomarkers per ARC criteria (periprocedural MI: CK-MB > 3x URL or Troponin > 3x URL within 48 hours after PCI; CK-MB > 5x URL or Troponin > 5x URL within 72 hours after CABG; Assessment of CK-MB is preferred over troponin for the diagnosis of periprocedural MI, if possible. For spontaneous MI: CK-MB > URL or Troponin > URL) (Circulation 2007; 116: 2344-2351)

**PROTOCOL ABT-CIP-10398 XIENCE 28 Global Study**

Point of Registration
	
Subject registration will occur after the index procedure but prior to discharge and up to 3 days post index procedure, upon confirmation of the following:
 
 • Signed informed consent has been obtained; • Subject has met all the inclusion and none of the exclusion criteria (including both general and angiographic criteria).

Subject Follow-Up
	
Subjects registered in the trial will receive the following clinical follow-up:
 
 • 1 month (28-35 days): office visit (Note: for subjects who have difficulty scheduling an office visit due to special circumstances, 1-month follow-up may be performed via telephone per physician's discretion) • 3 months (90 ± 7 days): office visit/telephone contact (office visit is strongly recommended whenever possible) • 6 months (180 ± 14 days): office visit/telephone contact (office visit is strongly recommended whenever possible) • 12 months (365 ± 28 days): office visit/telephone contact (office visit is strongly recommended whenever possible)

Primary Analysis Sample Size Justification
	
To further evaluate the safety of 1-month DAPT, non-inferiority (NI) will be tested comparing 1-month DAPT to XIENCE V USA historical control for the primary endpoint of NACE from 1- to 6-month follow-up in a "1-month clear" population (defined as subjects who are free from myocardial infarction [modified ARC], repeat coronary revascularization, stroke, or stent thrombosis [ARC definite/probable] within 1 month (prior to 1-month visit but at least 28 days) after stenting AND have been compliant with 1-month DAPT without interruption of either aspirin and/or P2Y12 receptor inhibitor for > 7 consecutive days).
 
[REDACTED]
 
[REDACTED]
 
[REDACTED]
 
[REDACTED]
 
[REDACTED]
 
[REDACTED]
 
[REDACTED]
 
[REDACTED]
 
[REDACTED]
 
[REDACTED]
 
[REDACTED]

PROTOCOL ABT-CIP-10398 XIENCE 28 Global Study

	
 • [REDACTED]

Antiplatelet Medication
	
Antiplatelet Medication Loading Dose:
 
 • Subjects must receive a loading dose of aspirin and/or a P2Y12 inhibitor (Clopidogrel, Prasugrel or Ticagrelor). The dosages of aspirin and P2Y12 inhibitor shall be determined by physician per standard of care and label indication for loading dose usage. The choice of P2Y12 inhibitor is per site standard of care, but clopidogrel is strongly recommended for HBR subjects. The loading of P2Y12 inhibitor can be omitted only if the subject is on chronic usage (≥ 7 days). Subjects that are not on chronic usage must be loaded with P2Y12 inhibitor. It is recommended that the subject be loaded with aspirin, even if the subject is on chronic usage of aspirin (≥ 7 days). 
Antiplatelet Medication Post-Procedure Daily Dose:
 
 • All subjects must receive ≥ 75 to ≤ 100 mg of aspirin daily throughout the trial. All subjects must maintain a minimum of 75 mg of clopidogrel daily or 5 or 10 mg of prasugrel daily (10 mg preferred in most subjects*) or 90 mg twice daily of ticagrelor for 1 month (as short as 28 days) following the procedure. 
 – The choice of P2Y12 inhibitor is per site standard of care, but clopidogrel is strongly recommended for HBR subjects. – For subjects taking chronic anticoagulants, dual therapy (oral anticoagulant and a P2Y12 inhibitor, clopidogrel preferred) may be considered within the first month per investigator’s discretion. • At 1-month follow up, subject will be assessed for their eligibility of P2Y12 inhibitor discontinuation. Eligible subjects will discontinue P2Y12 inhibitor as early as 28 days and receive ≥ 75 to ≤ 100 mg of aspirin daily through 1-year follow-up during the trial if they are “1-month clear”, defined as subjects who are free from myocardial infarction (modified ARC), repeat coronary revascularization, stroke, or stent thrombosis (ARC definite/probable) within 1 month (prior to 1-month visit but at least 28 days) after stenting AND have been compliant with 1-month dual antiplatelet therapy (DAPT) without interruption of either aspirin and/or P2Y12 receptor inhibitor for > 7 consecutive days. Subjects who were on dual therapy during the first month (anticoagulant and a P2Y12 inhibitor) will discontinue the P2Y12 inhibitor after 1 month. If they are assessed as “1-month clear”,

PROTOCOL ABT-CIP-10398 XIENCE 28 Global Study

	
these subjects will start aspirin and will be on aspirin and anticoagulant for the remainder of the trial.
 
If a subject was event-free and DAPT compliant (as defined above) during the first month, but does not stop P2Y12 inhibitor after the 1-month visit, due to physician’s or subject’s decision, this subject will be considered as “1-month not clear”.
 
[REDACTED]
 
[REDACTED]
 
[REDACTED]
 
[REDACTED]
 
[REDACTED]
 
[REDACTED]
 
 • Subjects who are not “1-month clear” are NOT eligible for P2Y12 inhibitor discontinuation. These subjects will be treated per the investigator's discretion and will continue to be followed up through 12 months. 
*For prasugrel subjects < 60 kg in weight or ≥ 75 years of age, a maintenance dose of 5 mg per day is allowable.

Cardiac Biomarker Collection
	
Cardiac biomarker CK, CK-MB and/or troponin collection shall be done per site’s standard of care. CK and CK-MB are preferred. If CK and CK-MB are not available, troponin should be collected.

Key Inclusion Criteria
	
General Inclusion Criteria
 
 1. Subject is considered at high risk for bleeding (HBR), defined as meeting one or more of the following criteria at the time of registration and in the opinion of the referring physician, the risk of major bleeding with > 1-month DAPT outweighs the benefit: 
 a) ≥ 75 years of age. b) Clinical indication for chronic (at least 6 months) or lifelong anticoagulation therapy. c) History of major bleeding which required medical attention within 12 months of the index procedure. d) History of stroke (ischemic or hemorrhagic). e) Renal insufficiency (creatinine ≥ 2.0 mg/dl) or failure (dialysis dependent). f) Systemic conditions associated with an increased bleeding risk (e.g. hematological disorders, including a history of or current thrombocytopenia defined as a platelet count

PROTOCOL ABT-CIP-10398 XIENCE 28 Global Study

<100,000/mm³, or any known coagulation disorder associated with increased bleeding risk).

g) Anemia with hemoglobin < 11g/dl.

2. Subject must be at least 18 years of age.
3. Subject must provide written informed consent as approved by the Ethics Committee (EC) of the respective clinical site prior to any trial related procedure.
4. Subject is willing to comply with all protocol requirements, including agreement to stop taking P2Y12 inhibitor at 1 month, if eligible per protocol.
5. Subject must agree not to participate in any other clinical trial for a period of one year following the index procedure.

Angiographic Inclusion Criteria

1. Up to three target lesions with a maximum of two target lesions per epicardial vessel. Note:
 - The definition of epicardial vessels means left anterior descending coronary artery (LAD), left circumflex coronary artery (LCX) and right coronary artery (RCA) and their branches. For example, the subject must not have >2 lesions requiring treatment within both the LAD and a diagonal branch in total.
 - If there are two target lesions within the same epicardial vessel, the two target lesions must be at least 15 mm apart per visual estimation; otherwise this is considered as a single target lesion.
2. Target lesion must be located in a native coronary artery with visually estimated reference vessel diameter between 2.25 mm and 4.25 mm.
3. Exclusive use of XIENCE family of stent systems during the index procedure.
4. Target lesion has been treated successfully, which is defined as achievement of a final in-stent residual diameter stenosis of <20% with final TIMI-3 flow assessed by online quantitative angiography or visual estimation, with no residual dissection NHLBI grade ≥ type B, and no transient or sustained angiographic complications (e.g., distal embolization, side branch closure), no chest pain lasting > 5 minutes, and no ST segment elevation > 0.5mm or depression lasting > 5 minutes.

PROTOCOL ABT-CIP-10398 XIENCE 28 Global Study

Key Exclusion Criteria

General Exclusion Criteria

1. Subject with an indication for the index procedure of acute ST-segment elevation MI (STEMI).
2. Subject has a known hypersensitivity or contraindication to aspirin, heparin/bivalirudin, P2Y12 inhibitors (clopidogrel/prasugrel/ticagrelor), everolimus, cobalt, chromium, nickel, tungsten, acrylic and fluoro polymers or contrast sensitivity that cannot be adequately pre-medicated.
3. Subject with implantation of another drug-eluting stent (other than XIENCE) within 12 months prior to index procedure.
4. Subject has a known left ventricular ejection fraction (LVEF) <30%.
5. Subject judged by physician as inappropriate for discontinuation from P2Y12 inhibitor use at 1 month, due to another condition requiring chronic P2Y12 inhibitor use.
6. Subject with planned surgery or procedure necessitating discontinuation of P2Y12 inhibitor within 1 month following index procedure.
7. Subject with a current medical condition with a life expectancy of less than 12 months.
8. Subject intends to participate in an investigational drug or device trial within 12 months following the index procedure.
9. Pregnant or nursing subjects and those who plan pregnancy in the period up to 1 year following index procedure. Female subjects of child-bearing potential must have a negative pregnancy test done within 7 days prior to the index procedure per site standard test.

Note: Female subjects of childbearing potential should be instructed to use safe contraception (e.g., intrauterine devices, hormonal contraceptives: contraceptive pills, implants, transdermal patches hormonal vaginal devices, injections with prolonged release.) It is accepted, in certain cases, to include subjects having a sterilised regular partner or subjects using a double barrier contraceptive method. However, this should be explicitly justified in special circumstances arising from the trial design, product characteristics and/or trial population

10. Presence of other anatomic or comorbid conditions, or other medical, social, or psychological conditions that, in the investigator’s opinion, could limit the subject’s ability to participate in the clinical investigation or to comply with follow-

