6.3.2 Antiplatelet Medications during Follow-up

- All subjects must receive ≥ 75 to ≤ 100 mg of aspirin daily throughout the trial. All subjects must maintain a minimum of 75 mg of clopidogrel daily or 5 or 10 mg of prasugrel daily (10 mg preferred in most subjects*) or 90 mg twice daily of ticagrelor for 1 month (as short as 28 days) following the procedure.
 - The choice of P2Y12 inhibitor is per site standard of care, but clopidogrel is strongly recommended for HBR subjects.
 - For subjects taking chronic anticoagulants, dual therapy (oral anticoagulant and a P2Y12 inhibitor, clopidogrel preferred) may be considered within the first month per investigator's discretion.
- At 1-month follow up, subject will be assessed for their eligibility of P2Y12 inhibitor discontinuation. Eligible subjects will discontinue P2Y12 inhibitor as early as 28 days and receive ≥ 75 to ≤ 100 mg of aspirin daily through 1-year follow-up during the trial if they are "1-month clear", defined as subjects who are free from myocardial infarction

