**PROTOCOL ABT-CIP-10398 XIENCE 28 Global Study**

(modified ARC), repeat coronary revascularization, stroke, or stent thrombosis (ARC definite/probable) within 1 month (prior to 1-month visit but at least 28 days) after stenting AND have been compliant with 1-month dual antiplatelet therapy (DAPT) without interruption of either aspirin and/or P2Y12 receptor inhibitor for > 7 consecutive days. Subjects who were on dual therapy during the first month (anticoagulant and a P2Y12 inhibitor) will discontinue the P2Y12 inhibitor after 1 month and if they are assessed as “1-month clear”. These subjects will start aspirin such that they will be on aspirin and anticoagulant for the remainder of the trial.

If a subject was event-free and DAPT compliant (as defined above) during the first month, but does not stop P2Y12 inhibitor after the 1-month visit, due to physician’s or subject’s decision, this subject will be considered as “1-month not clear”.

[REDACTED]

- Subjects who are not “1-month clear” are NOT eligible for P2Y12 inhibitor discontinuation. These subjects will be treated per the investigator's discretion and will continue to be followed up through 12 months.

*For prasugrel subjects < 60 kg in weight or ≥ 75 years of age, a maintenance dose of 5 mg per day is allowable.

The use of the above antiplatelet medications, including the start and stop date, any changes, as well as the reason to stop, will be documented in the eCRF.

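### For subjects on an anticoagulant plus a P2Y12 inhibitor in month 1, the Protocol Summary and Section 6.3.2 disagree on whether stopping the P2Y12 inhibitor depends on being 1-month clear

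*Protocol*

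**What the plan says.** Both places permit the regimen in the same terms: "dual therapy (oral anticoagulant and a P2Y12 inhibitor, clopidogrel preferred) may be considered within the first month", at the investigator's discretion, for subjects taking chronic anticoagulants. Both give the general rule for the 1-month visit: "Eligible subjects will discontinue P2Y12 inhibitor as early as 28 days and receive" aspirin, provided they are 1-month clear. In the visible definition, clear means free of MI, repeat revascularisation, stroke and stent thrombosis in month 1, and compliant with antiplatelet therapy in that month.

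They then differ on dual-therapy subjects.

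- **Protocol Summary, Antiplatelet Medication.** "Subjects who were on dual therapy during the first month (anticoagulant and a P2Y12 inhibitor) will discontinue the P2Y12 inhibitor after 1 month", followed by a full stop. A new sentence opens with the condition of being 1-month clear and continues: "these subjects will start aspirin and will be on aspirin and anticoagulant for the remainder of the trial".
- **Protocol Section 6.3.2.** The same subjects "will discontinue the P2Y12 inhibitor after 1 month and if they are assessed as" 1-month clear. A separate sentence follows: "These subjects will start aspirin such that they will be on aspirin and anticoagulant for the remainder of the trial".

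Both places close with a bullet stating that subjects who are not 1-month clear "are NOT eligible for P2Y12 inhibitor discontinuation", leaving their further treatment to the investigator. The visible text of that bullet makes no exception for dual therapy. Protocol Section 6.4 names Section 6.3.2 as the source of the criteria to be applied at the 1-month visit.

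**The concern.** The condition is attached to different acts. In the Summary it governs starting aspirin; in Section 6.3.2 it governs stopping the P2Y12 inhibitor. The sentences share their opening words, and the difference is where the first one ends.

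This matters because it is an operative instruction on stopping an antiplatelet drug, and it diverges for subjects who had an ischaemic event or a treatment interruption in month 1. Protocol Section 15.4 itself says that shorter DAPT may raise the risk of stent thrombosis and ischaemic events. The case is foreseeable: a clinical indication for chronic anticoagulation is high-bleeding-risk criterion (b) in Section 5.3.1.1. There is also a compliance side. Section 11.5 classes treatment compliance deviations as major, and for such a subject the text does not give one instruction against which compliance could be judged.

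**Working it through.** No arithmetic applies, and the plan gives no figure to reproduce. The check sets the visible statements side by side and follows each through the two possible cases.

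| Statement | Dual therapy, 1-month clear | Dual therapy, not 1-month clear |
|---|---|---|
| Summary, dual-therapy sentence | Stop P2Y12 inhibitor | Stop P2Y12 inhibitor |
| Summary, next sentence | Start aspirin, keep anticoagulant | Does not apply |
| Summary, closing bullet | Does not apply | Not eligible to stop |
| 6.3.2, dual-therapy sentence | Stop P2Y12 inhibitor | No stop directed |
| 6.3.2, next sentence | Start aspirin, keep anticoagulant | On the natural reading, does not apply |
| 6.3.2, closing bullet | Does not apply | Not eligible to stop |

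1. **Clear subjects.** Every applicable statement gives the same result. There is no conflict.
2. **Not-clear subjects.** The Summary's dual-therapy sentence directs a stop. The Summary's closing bullet and the 6.3.2 bullet say the subject is not eligible to stop, and the 6.3.2 sentence directs no stop. One visible statement stands against three, one of them in the same Summary cell. They cannot all be followed.
3. **Effect on the primary test.** Protocol Sections 9.1, 9.2 and 9.4.1 and SAP Sections 1.4 and 1.6 confine the test to the 1-month clear population. A subject who is not clear because of a month-1 event or interruption stays not clear whatever is done with the P2Y12 inhibitor afterwards. Following one sentence or the other therefore does not move that subject into or out of the primary analysis. The SAP Section 2.9 analyses described in the visible text are also confined to the 1-month clear population.
4. **Where it can show.** Section 6.4 keeps all registered subjects in follow-up through 12 months, and SAP Section 2.2.3 describes the secondary endpoints in all registered subjects as well as in the primary population. Not-clear dual-therapy subjects are in that wider set.

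**The case against.** The strongest reply is that the intent can be read from the context. The Summary sentence sits in a bullet that begins with an assessment of eligibility and with eligible subjects stopping. The next visible bullet bars not-clear subjects from stopping, and Section 6.4 points sites to Section 6.3.2. To be misled, a site would have to read one sentence apart from all of these. The sentence may be a slip of punctuation. The affected group is also narrow: chronic anticoagulation, an optional regimen actually chosen, and not clear at 1 month. It is not shown that any two sites would act differently.

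That stands, and it is why the point is minor. It does not make the instructions consistent. Redacted lines follow in both places and may add rules, but they cannot change the visible sentences.

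A reader might infer more in three places, and the documents do not support it.

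- **That a not-clear subject would be left with neither P2Y12 inhibitor nor aspirin.** The Summary pair, read alone, suggests this. However, the list opens with a requirement that all subjects receive a stated dose range in "mg of aspirin daily throughout the trial", and the closing bullet bars the stop.
- **That the wording for managing not-clear subjects is a second contradiction.** The closing bullets leave treatment to the investigator, while Appendix IV footnote 2 refers to site practice. An investigator can exercise judgement within site practice, so this is only a difference of wording.
- **That no dual-therapy subject could meet the compliance part of the 1-month clear definition, having had no aspirin in month 1.** Both dual-therapy passages presuppose that such subjects can be clear. Redacted text also follows the definition in Protocol Section 9.2 and SAP Section 1.4 and may settle it.

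**Conclusion.** The inconsistency is real and minor. For dual-therapy subjects who are not 1-month clear, the Summary sentence contradicts Section 6.3.2 and the Summary's own closing bullet. For those who are clear, there is no conflict.

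A reader might take this as a threat to the primary non-inferiority result. It is not, because these subjects are outside the primary population under either reading. This rests on the visible population definitions and assumes that the redacted text does not bring not-clear subjects into the test. What remains is the treatment of these subjects and, through it, the descriptive results in all registered subjects. The documents give neither the number on dual therapy nor the number not clear, so no numerical size is claimed.

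**What to change.** Reconcile the two passages. Put one identical statement in the Protocol Summary and Section 6.3.2 that says what happens to the P2Y12 inhibitor and to aspirin, separately for dual-therapy subjects who are 1-month clear and for those who are not. Make sure it agrees with the closing bullet in each place, and send sites a clarification. Which rule is right is for the sponsor and investigators to decide.

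The cost is a short wording change in two places, a site notice, and the ethics committee step that Protocol Section 11.2 requires for an amendment. No new data are needed: antiplatelet start and stop dates (Section 6.3.2) and oral anticoagulant use (Section 6.1.3) are already recorded.
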